#### 5.12.5 Brainstem

- D50% < 6100cGy and D10% < 6300cGy Goal
- D50% < 6200cGy and D10% < 6400cGy Maximum

St. Jude Children's Research Hospital

IRB NUMBER: Pro00004349
IRB APPROVAL DATE: 02/01/2023

- Comment Effort should be made to minimize dose to the brainstem without compromising target volume coverage. In the event that the recommended maximum dose constraints provided in this section would be exceeded, the treating radiation oncologist may use their discretion to reduce target volume coverage.
- Structure Definition The brainstem may be contoured on the treatment planning CT or MR and will include the midbrain, pons and medulla. The cranial extent will be inferior to the IIIrd ventricle and optic tracts. The caudal extent will end at the foramen Magnum. A brainstem core representing tissue  $\geq 3$ mm depth from the brainstem surface may be contoured when indicated.

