# 5.2 Treatment Planning and Specifics

The guidelines for this study were based on the experience treating patients with ependymoma at St. Jude Children's Research Hospital. This includes patients treated with radiation therapy at the time of initial diagnosis as well as recurrence after prior focal irradiation. Patients with local failure will be treated with surgery and a second course of focal irradiation. The total dose for the second course of irradiation for most cases will be 54Gy. The total dose may be attenuated for patients with prior history of significant treatment-related complications or in the setting of significant dose heterogeneity or high-dose treatment volumes. Patients with metastatic failure will be treated with metastasectomy and craniospinal irradiation. Craniospinal irradiation (36-39.6Gy) will include focal boost treatment of primary and metastatic sites (50.4-59.4Gy) depending on location, extent of resection and target volume. Patients with combined local failure will undergo metastasectomy, primary site resection and craniospinal irradiation.

Targeting the primary site for retreatment follows the principle of minimizing dose to normal tissue, irradiating only the site of known recurrent disease and not irradiating the entirely of the tumor bed at the time of initial diagnosis. It is anticipated that some tissues will receive a combined dose  $59.4 \text{Gy} + 54 \text{Gy} \sim 114 \text{Gy}$  from the first and second courses of irradiation, respectively.

The prescribed dose for ependymoma has evolved to a standard of 59.4Gy when using a clinical target volume margin of 1cm for all children except those under the age of 18 months treated with gross-total resection. There are ample data demonstrating that these prescribed doses and target volumes are reasonable and safe. In the setting of recurrent disease and prior irradiation, the dose of 59.4Gy is appropriate for previously untreated brain and the limit for previously irradiated tissue will be 54Gy. The neuraxis dose for metastatic ependymoma has been chosen to achieve the highest level of disease control; however, there may be instances when portions of the neuraxis will receive less than 36Gy owing to concerns about potential risks.

IRB Approval date:

Rev. 3.2 dated: 1/19/2023 Protocol document date: 1/19/2023 St. Jude Children's Research Hospital

IRB NUMBER: Pro00004349

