#### 5.9.2 Prescribed dose and fractionation

IRB Approval date: St. Jude Children's Research Hospital IRB NUMBER: Pro00004349

The patient should be treated with one fraction per day. All fields should be treated each day in photon treatments. Simultaneous integrated boost is not allowed.

Table Prescribed Doses and Fractionation

Total Dose by Site	Target Volume	Dose/fraction	Number of Fractions
Neuraxis 3600-3960CcGE/cGy	CTV CSI /PTV CSI	180CcGE/cGy	20-22
Primary Site 5040-5400cGy	CTV PS /PTV PS	180CcGE/cGy	10-30
Metastases 5040-5940cGy	CTV X /PTV X	180CcGE/cGy	5-13

The total dose to the target volume CTV (proton) or PTV (photon) prescription isodose surface will be 5400CcGE/cGy administered in 30 fractions of 180CcGE/cGy. The patient should be treated with one fraction per day. All fields should be treated each day in photon treatments. Exceptions will include unanticipated changes in patient's clinical condition, logistical considerations owing to holidays, weather, equipment failure and the need to complete the course of treatment in the least number of elapsed days. Two treatments in one calendar day will be discouraged. We will consider a single fraction reduction in the dose regimen for cases where significant dose heterogeneity are encountered. Investigator discretion may be used to alter the dose per fraction 150-200CcGE/cGy per day when indicated and requires PI approval. The total dose may be attenuated - 3420CcGE/cGy instead of 3600CcGE/cGy CSI or 5040CcGE/cGy instead of 5400CcGE/cGy primary site - for patients with prior history of significant treatment-related complications or in the setting of significant dose heterogeneity or high-dose treatment volumes. We will also consider alterating the craniospinal dose when there are concerns about excessive risks regarding treatment-related complications,

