#### 5.9.3 Dose Uniformity

Photon Therapy Goals: At least 95% of the protocol-specified dose should encompass 100% of the PTV and no more than 10% of PTV should receive greater than 110% of the protocol dose as evaluated by DVH. The 100% isodose should be equal to the protocol specified dose. All methods of generating more uniform dose distributions are encouraged. For craniospinal treatments, the dose will be measured at the midplane of the cranial volume and at the posterior border of the vertebral body the spinal field(s) including the dose at the central ray. Effort should be made to minimize inhomogeneity at the craniocervical junction when possible and the gradient of dose across the spinal cord.

IRB Approval date:

Rev. 3.2 dated: 1/19/2023 Protocol document date: 1/19/2023 St. Jude Children's Research Hospital

IRB NUMBER: Pro00004349

Proton Therapy Goals: At least 95% of the protocol-specified dose should encompass 100% of the CTV and no more than 10% of CTV should receive greater than 110% of the protocol dose as evaluated by DVH. The 100% isodose should be equal to the protocol specified dose. The PTV may be used to select the appropriate beam size and beam arrangements to achieve lateral coverage of the targeted volume and to minimize heterogeneity. The lateral margin for proton therapy should be approximately 3mm. The PTV will not be used to determine the distal range for the individual proton beams. The proton distal target margin will be determined per beam based on the distal aspect of the CTV and additional margin(s) meant to account for range uncertainty and the SM and IM components of the PTV which are understood for this group of patients and which may affect the proton distal range.‡

Proton Distal Target Margin† = CTV + Range Uncertainty + Set-up Margin + Internal Margin

- CTV = the distal aspect of the CTV
- Range Uncertainty = 3% of the water-equivalent range of the CTV at max depth
  - $\circ$  > 1mm
- Set-up Margin = set-up, mechanical, dosimetric and registration uncertainties
  - Protons are relatively unaffected by set-up uncertainty in axis of beam. Setup errors for brain in general do not have an impact on range per se.
  - Uncertainty in hardware and software no assigned value available
     Uncertainty in accuracy of image registration
    - > 1mm
- Internal margin = compensates for all variations in site, size and shape of the tissues contained in or adjacent to the CTV. We assume no internal organ motion.

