#### 5.12 Organs at Risk

The organs at risk guidelines in this section are recommendations. If the recommended doses to the organs at risk are exceeded because of target volume coverage requirements or other conditions, an explanation should be included in the quality assurance documentation. Note these guidelines are for the current treatment protocol and do not represent cumulative target doses.

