#### 5.12.3 Optic Nerves and Chiasm

- D50% < 5400cGy and D10% < 5600cGy Goal
- D50% < 5600cGy and D10% < 5800cGy Maximum
- Comment Effort should be made to avoid direct treatment of the optic nerves and chiasm without compromising target volume coverage. In the event that the recommended maximum dose constraints provided in this section would be exceeded, the treating radiation oncologist may use their discretion to reduce target volume coverage.
- Structure definition The optic nerve may be contoured on CT or MR. The contour should appear on at least two successive CT or MR images.

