#### **5.13.2** Normal Tissue Dosimetry

The dose to the critical organs indicated should be calculated whenever they are directly included in a radiation field. A DVH must be submitted for a category of tissue called "unspecified tissue," which is defined as tissue contained within the skin, but which is not otherwise identified by containment within any other structure. A DVH for "Body" shall be submitted to enable calculation of the required volumes. "Body" is defined as the outer contour of the patient on the treatment planning CT data set.

Required DVH data regardless of primary treatment site

Required DVH
Optic Chiasm
Brainstem
Spinal Cord
Right Cochlea
Left Cochlea
Body

IRB Approval date:

Rev. 3.2 dated: 1/19/2023 Protocol document date: 1/19/2023 St. Jude Children's Research Hospital

IRB NUMBER: Pro00004349

Unspecified Tissue

Treated Volume, Irradiated Volume and Conformity Index (CI) The treated volume (TV) is the tissue volume that receives therapeutic dose. For the purpose of this protocol this would include the prescribed total dose of 54-59.4Gy and 95% of the prescribed dose. This information may be used by the investigators, along with the absolute volume of the PTV, to calculate the conformity indexes (CI) CI100% and CI95%, respectively. The irradiated volume (IV) is the tissue volume that receives a dose that is considered significant in relation to normal tissue tolerance. The descriptive statistics for these and other tissue volumes maybe used for correlation with unusual side effects or to develop practical guidelines for future brain tumor protocols.

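### The required treated volumes in section 5.13.2 are set for a 59.4 Gy prescription, while most courses are 54 Gy; the brainstem values in 5.12.5 need their prescription stated

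*Combined protocol and SAP*

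**What the plan says.** **Prescription.** Section 5.2 gives most second courses a total of 54 Gy and separates two levels: "the dose of 59.4Gy is appropriate for previously untreated brain and the limit for previously irradiated tissue will be 54Gy". The dose table in section 5.9.2 lists "Primary Site 5040-5400cGy" and allows 50.4-59.4 Gy for metastases. The text below the table says that the "prescription isodose surface will be 5400CcGE/cGy administered in 30 fractions of 180CcGE/cGy", and permits attenuation to 50.4 Gy.

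**Treated volume.** Section 5.13.2 defines it by "the prescribed total dose of 54-59.4Gy and 95% of the prescribed dose". The list of required volumes then gives fixed thresholds: TV95% is V56.4 Gy and TV100% is V59.4 Gy. The same list asks for V35, V45 and V54 Gy as irradiated volumes. The section lets investigators combine treated volume with PTV volume into CI100% and CI95%, and lets the volumes be related to unusual side effects or feed future guidelines. It requires a DVH for the whole body contour.

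**Uniformity.** The photon goal in section 5.9.3 is that "no more than 10% of PTV should receive greater than 110% of the protocol dose". The proton goal is the same, set on the CTV.

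**Brainstem.** Section 5.12.5 has one set of values: a goal of D50% below 61 Gy and D10% below 63 Gy, and then "D50% < 6200cGy and D10% < 6400cGy Maximum". The opening of section 5.12 calls the organ-at-risk values recommendations for the current course, not cumulative doses. Where they are exceeded, "an explanation should be included in the quality assurance documentation".

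**The concern.** A treated-volume threshold should follow the prescription. If TV100% is read at 59.4 Gy in every patient, it shows coverage in a patient prescribed 59.4 Gy and the size of the hot spot in a patient prescribed 54 Gy. Pooled across patients, one variable name would carry two meanings, and the difference would track prescription level and therefore prior irradiation. Any conformity index or correlation with side effects would inherit that.

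The brainstem values show the same pattern. Section 2.1 puts brainstem necrosis among the investigators' greatest worries, and section 2.6.2 places brainstem and cerebellar tolerance at about 54-60 Gy, often already reached in the first course. Values of 61-64 Gy for the second course alone therefore invite the question of which prescription they were written for.

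**Working it through.** **1. Reproduce the listed thresholds.** TV95% = 0.95 x prescribed dose. With 59.4 Gy: 0.95 x 59.4 = 56.43, which is the listed V56.4. Backwards: 56.4 / 0.95 = 59.37. The list reproduces at 59.4 Gy (33 x 1.8 Gy) and not at 54 Gy (30 x 1.8 Gy).

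**2. Read the listed volumes at each prescription** (threshold / prescribed dose):

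| Prescription (Gy) | 95% level (Gy) | 110% level (Gy) | V56.4 is the | V59.4 is the | V54 is the |
|---|---|---|---|---|---|
| 50.4 | 47.88 | 55.44 | 111.9% volume | 117.9% volume | 107.1% volume |
| 54 | 51.30 | 59.40 | 104.4% volume | 110.0% volume | 100.0% volume |
| 59.4 | 56.43 | 65.34 | 94.9% volume | 100.0% volume | 90.9% volume |

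At 54 Gy the listed TV100% falls exactly on the hot-spot level of section 5.9.3.

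**3. Effect on a conformity index.** Take CI100% = TV100% / PTV; the section names the two inputs but prints no formula, so this is an assumption. A 54 Gy photon plan that meets the uniformity goal has at most 10% of the PTV above 1.10 x 54 = 59.4 Gy. If dose above that level stays inside the PTV, V59.4 / PTV is at most 0.10. For protons the same bound holds if that dose stays inside the CTV. A 59.4 Gy plan whose prescription isodose encloses the PTV gives about 1. Two good plans would then differ roughly tenfold for a reason unrelated to conformity. With V54 as the numerator, the 54 Gy plan also gives about 1.

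**4. Brainstem values as a percentage of prescription:**

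| Prescription (Gy) | 61 Gy | 62 Gy | 63 Gy | 64 Gy |
|---|---|---|---|---|
| 50.4 | 121.0 | 123.0 | 125.0 | 127.0 |
| 54 | 113.0 | 114.8 | 116.7 | 118.5 |
| 59.4 | 102.7 | 104.4 | 106.1 | 107.7 |

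All four lie above the 110% level at 54 Gy (59.4 Gy) and below it at 59.4 Gy (65.34 Gy). A cumulative reading does not explain them: section 5.12 excludes it, and two courses would sum to 59.4 + 54 = 113.4 Gy.

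**5. Comparison with a neighbouring structure.** The optic maximum, "D50% < 5600cGy and D10% < 5800cGy Maximum", is 56/54 = 103.7% and 58/54 = 107.4% of 54 Gy, inside the 110% level. At 50.4 Gy the same values are 111.1% and 115.1%, so a poor fit at the attenuated dose is not peculiar to the brainstem.

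**The case against.** **On treated volume.** The text of section 5.13.2 already defines the quantity by prescription, so an investigator who follows the text and not the list gets it right. V54 is collected as IV54, which is the 100% volume of a 54 Gy plan under another label. The Body DVH allows any other threshold to be recovered. The conformity index is optional, and no analysis in section 11 names treated volume or conformity; section 11.7 speaks of irradiated volume. All of this stands, and it is why the point is minor. It does not make the list correct: V51.3 for a 54 Gy plan, and both volumes for a 50.4 Gy plan, are not listed, and the two labels contradict the definition above them.

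**On the brainstem.** The values are recommendations. The 54 Gy limit for previously irradiated tissue, the uniformity goal and the instruction to minimise brainstem dose come first, and section 5.2 leaves the dose to previously irradiated brainstem to investigator discretion. This also stands.

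A reader might infer more than the documents support:

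- *That the brainstem values can bind only with a 59.4 Gy boost.* Section 5.10.7 allows a radiosurgery boost with brainstem dose below 12 Gy. In physical dose, 54 + 12 = 66 Gy, which passes 64 Gy. The uniformity goal also governs the target, not the brainstem, so weak constraint at 54 Gy is a practical inference and not a strict bound.
- *That every focal primary-site plan is affected.* A supratentorial target far from the brainstem is not touched by section 5.12.5.
- *That the plan permits overdose because 59.4 + 59.4 = 118.8 Gy exceeds the anticipated 114 Gy or so.* That sets a hot-spot sum against a sum of prescriptions.
- *That multiplying the brainstem values by 54/59.4 gives the right limits.* Nothing in the documents supports linear scaling as a tolerance for previously irradiated brainstem.

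**Conclusion.** The treated-volume list is wrong as written for any prescription other than 59.4 Gy. At 54 Gy it records the 110% and 104% volumes in place of 100% and 95%; at 50.4 Gy, the 118% and 112% volumes. Those percentages are plain arithmetic. The tenfold contrast in the conformity index also assumes the usual ratio and hot spots confined to the target.

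The impact is minor. No data need be lost, and the primary endpoint, sample size and necrosis stopping rule are unaffected.

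On the brainstem, what holds is narrower: one unlabelled set of values matches 59.4 Gy and gives little constraint on a 54 Gy plan. Whether previously irradiated brainstem needs a lower limit, and what it should be, is a clinical decision that the documents do not settle.

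**What to change.** **Section 5.13.2.** Replace the two fixed thresholds with TV100% = V(prescribed dose) and TV95% = V(95% of prescribed dose):

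- 54 Gy: V54 and V51.3
- 50.4 Gy: V50.4 and V47.9
- 59.4 Gy: V59.4 and V56.4, as now

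Extend the dose range in the definition down to 50.4 Gy so that attenuated courses are covered. Note that IV54 already holds V54. Where one patient has targets at different levels, record the prescription to which each treated volume refers. Recalculate past cases from the Body DVH before any conformity index or correlation is reported. The cost is one table edit and a recalculation.

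**Section 5.12.5.** Ask the sponsor's radiation oncologists to state which prescription the present values serve, and to choose any limits for previously irradiated brainstem on clinical grounds. Do not insert proportionally scaled numbers. The cost is one clarifying line, plus clinical review if new limits are wanted.

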#### 5.13 Dose Calculations and Reporting

#### 5.13.1 Prescribed Dose

The dose should be prescribed to an isodose surface that encompasses the CTV (proton) or PTV (photon) and allows the dose uniformity requirements to be satisfied.

#### **5.13.2** Normal Tissue Dosimetry

The dose to the critical organs indicated should be calculated whenever they are directly included in a radiation field. A DVH must be submitted for a category of tissue called "unspecified tissue," which is defined as tissue contained within the skin, but which is not otherwise identified by containment within any other structure. A DVH for "Body" shall be submitted to enable calculation of the required volumes. "Body" is defined as the outer contour of the patient on the treatment planning CT data set.

Required DVH data regardless of primary treatment site

Required DVH
Optic Chiasm
Brainstem
Spinal Cord
Right Cochlea
Left Cochlea
Body

IRB Approval date:

Rev. 3.2 dated: 1/19/2023 Protocol document date: 1/19/2023 St. Jude Children's Research Hospital

IRB NUMBER: Pro00004349

Unspecified Tissue

Treated Volume, Irradiated Volume and Conformity Index (CI) The treated volume (TV) is the tissue volume that receives therapeutic dose. For the purpose of this protocol this would include the prescribed total dose of 54-59.4Gy and 95% of the prescribed dose. This information may be used by the investigators, along with the absolute volume of the PTV, to calculate the conformity indexes (CI) CI100% and CI95%, respectively. The irradiated volume (IV) is the tissue volume that receives a dose that is considered significant in relation to normal tissue tolerance. The descriptive statistics for these and other tissue volumes maybe used for correlation with unusual side effects or to develop practical guidelines for future brain tumor protocols.

#### Required Volumetric Information

Required Volumes

TV95%=V56.4
Gy
TV100%=V59.
4Gy
IV35=V35Gy
IV45=V45Gy
IV54=V54Gy
PTV
CTV
GTV
Entire Brain
Unspecified
Tissue

#### 5.14 Patterns of Failure Evaluation

Protocol document date: 1/19/2023

The patterns of failure for patients with ependymoma may be described as local, distant or a combination of local and distant based on imaging evaluation of the neuraxis. Local failure is defined as progression or recurrence of tumor at the primary site of disease. Distant failure is defined as the progression or recurrence of tumor at a location other than the primary site. Distant failure most often occurs in the subarachnoid space and may occur at any point within the neuraxis. Although rare, extra-CNS metastasis represents distant failure. Combined local and distant failure is defined when evaluation of the entire neuraxis reveals synchronous local and distant failure.

Rev. 3.2 dated: 1/19/2023 IRB Approval date: St. Jude Children's Research Hospital IRB NUMBER: Pro00004349

The present study involves treatment of the primary site only, neuraxis with or without supplemental primary and metastatic site irradiation. Because the prescription dose will be confined to a limited volume encompassing the tumor and/or tumor bed, it is possible that the volume that receives the prescription dose will not subtend the entire area at risk and that the rate of failure for patients treated using the guidelines will be driven by targeting. Determining the patterns of failure will require an assessment of tumor recurrence with respect to targeting and dosimetry. Failure may be described as in-field, marginal or out-of-field when focal irradiation techniques are used. Out-of-field failure is recurrence that occurs entirely outside of the CTV and is synonymous with distant failure. In-field failure is recurrence that originated entirely within the volume that was targeted to receive the prescription dose (CTV). Marginal failure is recurrence originating on the margin of the volume targeted to receive the prescription dose (CTV) and may be described in terms of location or the dose received.

There is no universally accepted analytical method to assess pattern of failure and to determine whether failure is in-field, marginal or out-of-field. For this study, the pattern of failure will be assessed qualitatively and quantitatively by registering MR data obtained at the time of failure to the dosimetry from the original treatment plan. Failures will be determined qualitatively to be "in-field" when the recurrence appears to have originated from within and remains confined to the CTV, "marginal" when a portion of the recurrence is within the CTV but the majority of the recurrence is outside of the CTV, "distant" when the recurrence does not involve the CTV. Recurrences will be quantitatively categorized as in-field, marginal, or out-of-field based on the proportion of the recurrence that received at least 95% of the prescription dose. This requires contouring of the recurrence and computation of the dose-volume histogram. Marginal failure occurs when between 20 and 80% of the recurrence volume receives more than 95% of the prescription dose, thus, in-field failure occurs when more than 80% of the recurrence volume receives more than 95% of the prescription dose and out-of-field failure occurs when less than 20% of the volume received more than 95% of the prescription dose. Any method has limitations; however, since the point of origin for tumor recurrence cannot be ascertained with absolute certainty and does not explicitly determine marginal failure. Because of this finding, we are not certain of the best method to define the patterns of failure at this time.

